3.1.1 Discontinuation criteria before the multiple dose period at each cohort

Prior to the multiple dose phase at each dose level, the safety results up to 72 hours after the single dose on Day 1 will be evaluated by the principal investigator. All safety related results will be reviewed for each subject. The review will include the following:

- All complete and brief physical examinations
- Laboratory tests
(The laboratory tests at the 48-hours post dose on Day 3 will be performed for the subjects who have significant abnormalities at the 24-hours post dose on Day 2.)
- Pulse, blood pressure (BP), body temperature (BT) and ECG
- The presence and type/intensity of AE
- Bleeding times

Subjects will be discontinued if any of the following symptoms are observed.

1. Aspartate aminotransferase (AST) and/or alanine aminotransferase (ALT) increase ≥ 3 times upper limit of reference range at the study center for which the causality of AZD6140 can not be excluded
2. Significant prolongation of the bleeding time (e.g. >30 minutes increase compared to baseline), as judged by the investigator, together with moderate to severe bleeding events and/or significant abnormalities of laboratory findings/vital signs, for which the causality of AZD6140 can not be excluded
3. Severe and serious adverse events for which the causality of AZD6140 can not be excluded

After the safety of the subjects is confirmed, the principal investigator will allow the subjects to enter the repeated dosing period (Refer to Section [3.3.5.1](#)).

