3. STUDY PLAN AND PROCEDURES

3.1 Overall study design

This will be a single-blind, randomized, placebo-controlled, Phase I study in healthy male Japanese and Caucasian subjects, performed at 2 study centers – Japanese in Japan and Caucasians in the US. The study will consist of two sequential study cohorts at each study center with 3 visits (a screening visit, a dosing/PK visit and a follow-up visit) for each cohort. (See [Figure 1](#)) A total of 72 subjects (36 Japanese and 36 Caucasian) will be randomized to AZD6140 or placebo. There will be 18 subjects within each cohort at each study center.

In each ethnic group, 36 healthy male subjects will be divided into two sequential cohorts of 18 subjects. Within each cohort, 15 subjects will receive AZD6140 and 3 subjects will receive placebo.

On Days 1 and 10, investigational products will be administered orally following a 10-hour overnight fast and subjects will remain fasting 4 hours post dose. On Days 4-9, subjects will receive AZD6140 or matching placebo at least 1 hour prior to having a meal.

The subjects for Cohort A in each center will be randomized to receive either AZD6140 or placebo before the morning dose on Day 1 of Visit 2. Subjects will receive a single 100 mg dose of AZD6140 (n=15 at each study center) or matching placebo (n=3 at each study center) on Day 1. Prior to dosing in the morning of Day 4, the principal investigator will evaluate the safety of each subject, based on all results of the safety assessment as well as the presence and type/intensity of adverse event (AE). After the safety for the subjects is confirmed, the principal investigator will allow the subjects to enter the multiple dose period (See [Section 3.1.1](#) and [Section 3.3.5.1](#)). **At the Japanese study center** the principal investigator will record the results of this safety confirmation. From Days 4-9, subjects randomized to AZD6140 will receive 100 mg AZD6140 bid and subjects randomized to placebo will receive matching placebo bid. On Day 10, subjects will receive a single 100 mg dose of AZD6140 or matching placebo in the morning only.

Prior to dosing subjects assigned to Cohort B, the safety results of Visit 2 in Cohort A will be evaluated by the principal investigator at each study center and the appropriate AstraZeneca study team physician of AstraZeneca. Refer to [section 3.1.2](#) for specific stopping criteria.

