Bleeding times								✓						✓							✓			
Randomization									✓															
AZD6140/Placebo administration									✓															
Adverse event recording	<-	--	--	--	--	--	--	--	--	--	--	--	--	--	--	--	--	--	--	--	--	--	--	
Genotyping blood sample ⁷⁾								✓																
Meal ⁸⁾	D				L		D							L		D		B	L	D				

- 1) Within 2 hours before AZD6140/Placebo administration
- 2) “Open, standardized AE questioning” will also be performed at the same time.
- 3) Japanese subjects only
- 4) Caucasian subjects only
- 5) Serial ECGs (two ECGs approximately 1 minute apart will be measured at each of these timepoints) will be recorded.
- 6) Faecal samples collected on Day –2 and during the period between 12h and 60h after dosing on Day 1 will be tested.
- 7) A single blood sample for genetic analysis will be obtained prior to dosing on Day 1 (See Appendix E).
- 8) Standardized meals, breakfast (B), lunch (L) and dinner (D), will be served after performing all assessments at each time point.

Table 3 Schedule of assessments Days 3, 4, 5, 6, 7, 8 and 9 of Visit 2

Study day	Day 3			Day 4									Day 5					Days 6 ~ 9							
	48h	52h	60h	Pre-dose	0h	1h	2h	4h	5h	8h	12h	13h	Pre-dose	0h	1h	5h	12h	13h	Pre-dose	0h	1h	5h	12h	13h	
Concomitant medication	--	--	--	--	--	--	--	--	--	--	--	--	--	--	--	--	--	--	--	--	--	--	--	--	--
Complete physical exam ¹⁾				✓ ³⁾																					
Brief physical exam ^{1,2)}	✓						✓	✓		✓			✓ ³⁾							✓ ³⁾					
12-lead ECG				✓ ³⁾									✓ ^{2,3)}							✓ ^{2,3)}					
Blood pressure, pulse	✓			✓ ³⁾									✓ ³⁾							✓ ³⁾					
Body temperature	✓			✓ ³⁾									✓ ³⁾							✓ ³⁾					
Haematology/clinical chemistry, urinalysis	(✓) ⁶⁾			✓ ⁴⁾																✓ ^{4,5)}					
Haemocult test ^{2, 7)}	--	--	->																						
PK blood samples	✓			✓ ⁴⁾																✓ ⁴⁾					
AZD6140/Placebo administration					✓						✓			✓			✓			✓				✓	
Adverse event recording	--	--	--	--	--	--	--	--	--	--	--	--	--	--	--	--	--	--	--	--	--	--	--	--	--
Meal ⁸⁾	B	L	D			B			L			D			B	L		D			B	L		D	

- 1) "Open, standardized AE questioning" will also be performed at the same time.
- 2) Japanese subjects only
- 3) Within 2 hours before AZD6140/Placebo administration
- 4) Just before dosing
- 5) Day 7 only
- 6) The laboratory tests at the 48-hours post dose on Day 3 will be performed for the subjects who have significant abnormalities at the 24-hours post dose on Day 2.

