4.4.3.2 Hematology

Hematology assessments will include the following:

Red blood cell (RBC), platelets, hemoglobin, hematocrit, white blood cell (WBC) and differential count (neutrophils, lymphocytes, monocytes, eosinophils and basophils), prothrombin time and activated partial thromboplastin time.

For the Japanese study center, the samples for prothrombin time and activated partial thromboplastin time will be sent to and analysed at SRL Nishinohon, Inc.

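### The Day 4 decision to start multiple dosing calls for safety results up to 72 hours, but the 72-hour AST/ALT sample is scheduled immediately before the dose it should inform

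*Supplement*

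**What the plan says.** Three parts of the protocol bear on the point.

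- **The gate.** Section 3.1.1 asks for an evaluation: "Prior to the multiple dose phase at each dose level, the safety results up to 72 hours after the single dose on Day 1" are to be assessed by the principal investigator. It adds "All safety related results will be reviewed for each subject" and lists laboratory tests among the items. The first discontinuation criterion is "Aspartate aminotransferase (AST) and/or alanine aminotransferase (ALT) increase ≥ 3 times upper limit of reference range" where a causal role of AZD6140 cannot be ruled out. Subjects go on to repeated dosing only once safety is confirmed.
- **When the gate applies.** For Cohort A, Section 3.1 says: "Prior to dosing in the morning of Day 4, the principal investigator will evaluate the safety of each subject, based on all results". Cohort B has a parallel instruction.
- **The schedule.** In Table 3 the single Day 4 haematology, chemistry and urinalysis draw carries footnote 4, "Just before dosing". The Day 4 physical examination, ECG, blood pressure, pulse and temperature carry footnote 3, which allows a two-hour window ahead of the dose.

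Amendment 1 alters blood volumes only and leaves all of this in force.

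**The concern.** A result can support a go/no-go decision only if it is reported before the decision. The bedside checks have time to be read. The laboratory sample, on which the AST/ALT criterion depends, has almost none. Followed literally, the schedule gives the site two options: dose without a result that Section 3.1.1 requires, or wait and depart from the planned timing.

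A transaminase rise first visible after 24 hours could then go unrecognised until multiple dosing had begun. Section 3.2 leans on this safeguard. It describes the treatment relationship of the earlier liver findings as not well established, names Day 4 among the liver-test days, and makes the Section 3.1.1 evaluation a condition for each subject to proceed.

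**Working it through.** This is schedule arithmetic. No sample size, power or error rate is involved.

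**1. The plan's own interval.** Section 3.2 states 72 hours between the single dose and the first multiple dose. From the study days: (4 − 1) × 24 h = 72 h. The figure is reproduced, so the 72-hour time point and the Day 4 pre-dose time point are the same.

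**2. Laboratory samples before the Day 4 dose (Tables 1 to 3).**

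| Sample | Who has it | Age at the Day 4 dose |
|---|---|---|
| Day −1 and Day 1 pre-dose | everyone | before any drug |
| 24 h (Day 2) | everyone | 72 − 24 = 48 h |
| 48 h (Day 3) | only if significantly abnormal at 24 h | 72 − 48 = 24 h |
| 72 h (Day 4) | everyone | drawn immediately before the dose |

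**3. Time between draw and dose.** No window in minutes is given for safety laboratory draws. Section 4 places the safety sample after the PK sample when both fall at one time point. The Day 4 PK sample carries the same footnote 4, and Table 6 gives the 72-hour PK sample a tolerance of ± 15 minutes. If the dose is given at its planned 72 hours, the laboratory draw therefore leads it by at most about 15 minutes.

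**4. Doses given before the 72-hour result is known.** Table 3 marks administrations at 0 h and 12 h. Let T be the turnaround time, which the documents do not give, and assume that the dose is not held. For T longer than the lead in step 3, the number of doses given is the whole-number part of T/12, plus 1.

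| Assumed T | Doses before the result |
|---|---|
| within the minutes between draw and dose | 0 |
| longer than that, under 12 h | 1 |
| 12 h to under 24 h | 2 |
| 24 h, with the Day 5 morning dose given | 3 |

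**5. Is the Day 4 sample meant to count?** Section 3.1.1 reaches to 72 hours and covers all safety results. It also lists all complete physical examinations, and in Tables 1 to 3 the only complete examination between the Day 1 dose and multiple dosing is the Day 4 pre-dose one. The gate therefore takes in the Day 4 pre-dose assessments.

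**The case against.** The strongest reply is that the gate is conditional. Entry is allowed only after safety is confirmed, so an investigator could hold the dose until the result arrives. That wording does stop short of telling the site to dose without the result. But no delay is provided for, Section 3.2 fixes the interval at 72 hours, and a sample followed by a wait would no longer be one taken "Just before dosing". The reply moves the conflict without removing it.

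A second reply is that the laboratory item in Section 3.1.1 mentions only the 24-hour test and its conditional 48-hour repeat, so the Day 4 draw may be just a baseline for the multiple-dose phase. The 72-hour limit and the sentence "All safety related results will be reviewed for each subject" weigh decisively against that.

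A third reply concerns consequence, and much of it stands. The 24-hour result is available to the investigator, and a 48-hour result where triggered. Section 3.3.5.1 applies the AST/ALT rule throughout treatment. The Day 4 result is still obtained, and testing recurs on Days 7, 10, 11 and 13. The transaminase rises described in Section 1.1 followed repeated dosing.

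Three stronger readings are tempting and are not supported:

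- That the 72-hour result can never inform the decision. This depends on a turnaround time that the documents do not state.
- That shipment of samples from the Japanese centre shows AST/ALT would be late. Section 4.4.3.2 says "the samples for prothrombin time and activated partial thromboplastin time will be sent to and analysed at" an outside laboratory. That covers coagulation tests and not transaminases.
- That all 72 subjects are exposed to the risk. Section 6.5 assigns 4 × 3 = 12 of them to placebo, in whom AZD6140 cannot cause a rise, and subjects with a significant 24-hour abnormality have a later sample.

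**Conclusion.** The concern holds as an inconsistency within the current text. Sections 3.1 and 3.1.1 require results that Table 3 schedules too late to be in hand, unless chemistry is reported within minutes of the draw. That proviso is the one inference involved. The two-hour allowance for the bedside checks, with none for the laboratory sample, supports it.

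In that case, for any subject without a significant 24-hour abnormality, the AST/ALT criterion would be judged on a result 48 hours old. A rise first detectable at 72 hours would be found after one dose if turnaround is under 12 hours, or two if it is 12 to under 24 hours, assuming 12-hourly dosing and no hold. The 24-hour data and Section 3.3.5.1 limit the harm, but they do not make the stated pre-dose gate workable. Sample size, power and type I error are unaffected.

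**What to change.** Reconcile the Day 4 laboratory draw time in Table 3 with the results that Sections 3.1 and 3.1.1 require for the Day 4 decision, so that every required result can be available before the dose. Both cohort paragraphs in Section 3.1 need to agree with the outcome. Whether the schedule or the list of required results changes is for the sponsor's physicians to decide. Stating the expected laboratory turnaround at each centre would let a reader confirm that the reconciled text can be followed.

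The cost is a footnote or text amendment and, at most, a blood draw at a different time in subjects who are already resident at the centre.

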The subjects for Cohort B will be randomized to receive either AZD6140 or placebo before the morning dose on Day 1 of Visit 2. Subjects will receive a single 300 mg dose of AZD6140 (n=15 at each study center) or matching placebo (n=3 at each study center) on Day 1. Prior to dosing in the morning of Day 4, the principal investigator will evaluate the safety results for each subject, based on all results of the safety assessment as well as the presence and type/intensity of AE. After the safety results for the subjects are confirmed, the principal investigator will allow the subjects to enter the multiple dose period. (See [Section 3.1.1](#) and [Section 3.3.5.1](#)) **At the Japanese study center** the principal investigator will record the

results of this safety confirmation. From Days 4-9, subjects randomized to AZD6140 will receive 300 mg AZD6140 bid and subjects randomized to placebo will receive matching placebo bid. On Day 10, subjects will receive a single 300 mg dose of AZD6140 or matching placebo in the morning only.

At Visit 2, subjects will remain at the study center for 72 hours following the last dose of investigational product. A follow-up visit (Visit 3) will be scheduled within 5 to 10 days following the last dose of AZD6140 or placebo.

The schedules of procedures and assessments are shown in [Table 1-Table 4](#).

Visit 1 Screening Period

In order to establish eligibility to participate in this study, subjects will undergo all screening procedures and assessments within 3 to 28 days prior to the first dosing of Visit 2. Subjects will have the study design fully explained to them. Each subject will provide written informed consent **prior** to any study related procedures or assessments.

Please refer to [Table 1](#) and [Section 4](#) for detailed descriptions of the screening assessments.

Visit 2 (Days –2 to 13)

Subjects will arrive at the study center on Day –2 as directed. At this time the subjects will be reassessed with regard to the study inclusion/exclusion criteria. On the morning of Day –1 baseline serial ECGs will begin.

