3.1.2 Stopping criteria for dose escalation

Prior to dosing in Cohort B, the safety results up to 72 hours after the final dose of Visit 2 in Cohort A will be evaluated by the principal investigator and study team physician of AstraZeneca in each site. **In Japan**, written approval from the sponsor will be obtained before dose escalation. Adverse events and all the other safety related data, with particular attention to events that may be caused by increases in bleeding times, clinical safety labs, and clinically significant changes in ECGs will be reviewed for Cohort A. If it is anticipated that subjects may experience risk from further dose escalations, then the escalation to the next dose group may be stopped after discussions between the principal investigator and the sponsor's physician have taken place.

The dose escalation for Cohort B will be discontinued if any of the following tolerability or safety symptoms occur in at least three individuals who received AZD6140.

- AST and/or ALT increase ≥ 3 times upper limit of reference range at the study center for which the causality of AZD6140 can not be excluded
- Significant prolongation of the bleeding time (e.g. >30 minutes increase compared to baseline), as judged by the investigator, together with moderate to severe bleeding events and/or significant abnormalities of laboratory findings/vital signs, for which the causality of AZD6140 can not be excluded

The discontinuation of dose escalation will be considered if the following tolerability or safety symptoms occur in at least one subject.

- Severe and serious adverse events for which the causality of AZD6140 cannot be excluded

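### Two stopping criteria (3.1.1 item 3 and the one-subject bullet of 3.1.2) join severe and serious with *and*, so read literally a related SAE below severe intensity falls outside the mandatory rule before bid dosing

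*Supplement*

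**What the plan says.** Section 3.1.1 governs the step from the single Day 1 dose to twice-daily dosing on Day 4. Its list is mandatory: "Subjects will be discontinued if any of the following symptoms are observed". The three items are:

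1. AST and/or ALT at least 3 times the upper reference limit, AZD6140 causality not excluded.
2. Significant bleeding-time prolongation "together with moderate to severe bleeding events and/or significant abnormalities of laboratory findings/vital signs", AZD6140 causality not excluded.
3. "Severe and serious adverse events for which the causality of AZD6140 can not be excluded".

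The section closes with a positive condition, followed by a reference to Section 3.3.5.1: "After the safety of the subjects is confirmed, the principal investigator will allow the subjects to enter the repeated dosing period". Section 3.1 repeats the condition for Cohort A ("After the safety for the subjects is confirmed, the principal investigator will allow the subjects to enter the multiple dose period") and Cohort B ("After the safety results for the subjects are confirmed, the principal investigator will allow the subjects to enter the multiple dose period"), each time citing both 3.1.1 and 3.3.5.1.

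Section 3.1.2 says that stopping escalation will be considered if at least one subject has "Severe and serious adverse events for which the causality of AZD6140 cannot be excluded".

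Section 3.3.5.1 item 2 gives a severe *or* serious AE as an example of a safety reason for which a subject may be discontinued, and refers to 3.1.2. Section 4.7.1 defines severe as intensity grade 3 (incapacitating) and leaves seriousness to Appendix B. It states that a severe AE need not be serious and that a stroke with limited disability may be mild yet still an SAE. Amendment No. 1 changes only blood volumes, so this wording is current.

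**The concern.** The protocol asks staff to keep severity and seriousness apart, then joins them with *and* in the one AE criterion that obliges a subject to stop before repeated dosing. A reader who applies the 4.7.1 definitions strictly would conclude that both must be present.

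On that reading, some events that most sponsors would want to stop dosing do not oblige it. The mild stroke of 4.7.1 is one. Appendix B gives others as examples of SAEs: angioedema that needs intravenous hydrocortisone but not intubation, and allergic bronchospasm treated intensively in an emergency room or at home. Either could be graded below severe, and neither by itself meets the transaminase or bleeding-time item. Appendix B also says that the sponsor would not normally support a rechallenge, which is what continuing after a related SAE on Day 1 would amount to.

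The criteria carry weight in this design. Section 3.2 relies on both sets when it justifies the first multiple dosing in Japanese subjects, and Section 6.8 provides no safety monitoring committee.

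**Working it through.** The plan gives no figure on this point, so the check is mainly textual.

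**Side by side**

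| Place | Connective | Force |
|---|---|---|
| 3.1.1 item 3 | and | mandatory discontinuation before Day 4 dosing |
| 3.1.2, one-subject bullet | and | stopping escalation is considered |
| 3.3.5.1 item 2 | or | discretionary, given as an example |

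**The four combinations, for an AE whose relation to AZD6140 cannot be excluded**

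| Event | *and* read as requiring both | *or*, as in 3.3.5.1 |
|---|---|---|
| Severe and serious | criterion met | criterion met |
| Serious, mild or moderate | not met | met |
| Severe, not serious | not met | met |
| Neither | not met | not met |

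The second row is the gap. It narrows where another item applies: a moderate serious bleed with significant bleeding-time prolongation already meets 3.1.1 item 2.

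**How often could it arise?** Section 1.1 reports no SAE in 11 completed Phase I studies, with 195 subjects exposed to AZD6140 in the 9 that were unblinded and/or reported.

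- One-sided 95% upper bound for 0 of 195: 1 − 0.05^(1/195) = 0.0152, or 1.5% per subject.
- Expected SAEs at that bound, assuming comparable risk: 15 × 0.0152 = 0.23 (AZD6140 subjects in one cohort at one center); 30 × 0.0152 = 0.46 (one center); 60 × 0.0152 = 0.91 (all planned AZD6140 subjects).
- The range is therefore 0 to about 0.9 SAEs of any cause over the whole study. SAEs that are also possibly drug-related, below severe intensity, within 72 hours of one dose and outside items 1 and 2 would be fewer. The documents do not allow that number to be worked out.

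**Where the wording applies**

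- Decisions to enter multiple dosing: 2 cohorts × 2 centers = 4 rounds.
- Escalation decisions: 1 per center × 2 centers = 2.
- Doses remaining for a subject who passes the Day 4 check: 6 days × 2 + 1 = 13.

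**The case against.** The strongest reply is that the gap exists only under the less natural reading. The plural phrase can mean severe events and serious events alike. Section 3.3.5.1 item 2 uses *or* and points to 3.1.2, the very section said to be narrower. Section 3.1.1 and both cohort paragraphs of 3.1 point to 3.3.5.1, so the *or* wording is brought in at the Day 4 decision itself. This largely stands as evidence of intent. It does not settle the text: items 1 and 2 of the same list write *and/or* where alternatives are meant, item 3 has a bare *and*, and 3.3.5.1 says only that a subject may be discontinued.

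Second, judgment already covers the case. Nobody proceeds to Day 4 dosing until the investigator confirms safety. Section 3.1.2 requires review of all Cohort A safety data with the sponsor's physician and allows escalation to stop on anticipated risk. Section 4.7.2 sends every SAE to the sponsor by the end of the next business day, and Section 5.7 has the sponsor re-examine continuation when it obtains safety information. This stands, and for 3.1.2 it leaves almost nothing lost, because the bullet only prompts consideration.

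A reader might infer two stronger things. One is that a subject with a mild related SAE would go on to bid dosing unchecked. The documents do not support this: the investigator would have to certify that subject as safe and the sponsor, though informed, would have to leave that decision in place. The other is that the US center could apply the rule differently without trace, because only the Japanese center is told that "the principal investigator will record the results of this safety confirmation" and to have written sponsor approval for escalation. That goes too far. At both centers, 4.7.1 requires causality, action taken, seriousness and any resulting discontinuation to be reported for each AE, and 4.7.2 puts every SAE in the CRF. Section 3.4.2 makes Cohort B wait for approval to escalate without limiting this to Japan, and 3.1 involves the sponsor's physician for each center. Only the separate Day 4 record and the written form of the approval are specific to Japan.

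**Conclusion.** The inconsistency is real and current. Read literally, 3.1.1 item 3 does not oblige discontinuation for a possibly drug-related SAE of mild or moderate intensity unless item 1 or 2 applies, and the one-subject bullet of 3.1.2 does not list it. What is lost is mainly the mandatory force of 3.1.1; the loss in 3.1.2 is an explicit prompt within a review that takes place anyway. The conclusion rests on *and* being read as requiring both properties, which the wording permits but the cross-references do not favor.

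The consequence is small. At most about 0.9 SAEs of any cause are expected among the 60 AZD6140 subjects at the 1.5% upper bound, assuming risk comparable with the earlier studies, and relevant events would be fewer. No endpoint, estimand or sample size changes. It should still be corrected, because a mandatory safety rule ought not to depend on inference and the repair is cheap.

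**What to change.** In 3.1.1 item 3 and the one-subject bullet of 3.1.2, replace the opening words with *Serious adverse events of any intensity* and leave the causality clause as it stands. This captures every possibly related SAE and leaves severe non-serious AEs to judgment under 3.3.5.1.

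If the sponsor also wants related severe, non-serious AEs to trigger both rules, write *Severe or serious adverse events* instead, which matches 3.3.5.1. That is the sponsor's choice. The downside is that an event such as the severe nausea of 4.7.1, if possibly related, would then oblige the subject to stop before Day 4 or prompt consideration of stopping escalation. Either version would gain from a reference to Section 4.7.1 and Appendix B for the definitions.

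The cost is one phrase in two places of an amendment, with no effect on data collection or analysis.
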